Part B of the project investigates the ability versus placebo of an isoprenaline infusion to induce atrial fibrillation and also any change in that inducibility associated with different ablation procedures. Subjects will be recruited based on their medical history and need for an ablation procedure. Subjects will be randomised in a double blinded fashion to receive isoprenaline or placebo infusions. The study drug infusion that they are randomised to will be delivered before and after their clinically indicated ablation procedure in the cardiac catheter laboratory environment whilst the subject is under sedation for that procedure. There will be follow up requirements for study subjects over and above the standard clinical follow up procedure.

Endpoints

Study Endpoints

Experiments 1, 5 and 6

Primary Endpoint

• Change in outcome between two administrations of the study drug infusion protocol **Secondary Endpoints**

- Change in time to outcome between two administrations of the study drug infusion protocol
- Change in maximum rate of infusion between two administrations of the study drug infusion protocol

Experiments 2, 3 and 4

Primary Endpoints

- Frequency of the occurrence of atrial fibrillation lasting greater than 30 seconds during study drug infusion protocol
- Frequency of the occurrence of an arrhythmia other than atrial fibrillation, sinus tachycardia or junctional rhythm lasting greater than 30 seconds during study drug infusion protocol

Secondary Endpoints

- Frequency of the occurrence of atrial fibrillation lasting less than 30 seconds during study drug infusion protocol
- Frequency of the occurrence of an arrhythmia other than atrial fibrillation, sinus tachycardia or junctional rhythm lasting less than 30 seconds during study drug infusion protocol
- Time from start of infusion protocol to occurrence of atrial fibrillation
- Rate of infusion at time of occurrence of atrial fibrillation
- Maximum tolerated rate of study drug infusion prior to its cessation for any reason

Infusion Endpoints

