All parts of this investigation utilise a standard infusion protocol of a study drug. This study drug will be isoprenaline or placebo delivered in a double blinded fashion or will be open label isoprenaline dependent on which experiment it is being administered for. In all cases the infusion protocol will be identical as will the associated outcomes recorded. Although different experiments within the protocol call for different, statistically driven endpoints, the endpoints for every administration of a study drug infusion protocol are the same.

Outcome after which infusion would be stopped

- Occurrence of atrial fibrillation lasting greater than 30 seconds during study drug infusion protocol
- Occurrence of an arrhythmia other than atrial fibrillation, sinus tachycardia or junctional rhythm lasting greater than 30 seconds during study drug infusion protocol
- Discontinuation of the study drug infusion
 - o Severe tremulousness or anxiety
 - Complaints of severe chest tightness
 - Decrease in systolic blood pressure to consistently < 70mmHg
 - Electrocardiographic changes suggestive of myocardial ischaemia

Pre-specified outcomes to be recorded but which would not trigger cessation of infusion

- Occurrence of atrial fibrillation lasting less than 30 seconds during study drug infusion protocol
- Occurrence of an arrhythmia other than atrial fibrillation, sinus tachycardia or junctional rhythm lasting less than 30 seconds during study drug infusion protocol
- Time from start of infusion protocol to occurrence of atrial fibrillation
- Rate of infusion at time of occurrence of atrial fibrillation
- Maximum tolerated rate of study drug infusion prior to its cessation for any reason

Safety Endpoints associated with each infusion administration

- Death within 24 hours of start of study drug infusion protocol
- Stroke within 24 hours of start of study drug infusion protocol
- Myocardial Infarction within 24 hours of start of study drug infusion protocol

Observational Data

Collected from Additional Monitoring Group

Participants from some groups recruited will be offered the chance to have some additional follow up monitoring after their ablation procedure. This data will be purely descriptive and unpowered. It will be analysed looking at the following endpoints.

Observational Endpoints

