The minimum staff required to administer the infusion will include a registered nurse considered competent with administration of intravenous medications (as judged by the hospital trust at which the infusion is being delivered) and a licensed medical practitioner considered experienced in the field of cardiology and who is a certified Advanced Life Support provider.

Prior to administration of the study drug infusion, the study team will assess the participant regarding their potential suitability for use of antiarrhythmic medications in the event that atrial fibrillation which persists for greater than 10 minutes is induced.

The route of administration will depend on the situation in which the infusion is being administered. Where the infusion is being administered in a ward based environment, it is anticipated that the infusion will be delivered via a peripherally sited intravenous cannula usually sitting in an antecubital fossa vein. Where the infusion is being given in the Cardiac Electrophysiology Laboratory, it will usually be administered via a central venous sheath sited in the femoral vein. Standard aspetic technique associated with the administration of intravenous drugs will be applied in all settings to comply with local policy.

The study drug infusion will be delivered following a modified version of the scheme previously published by Morady and colleagues(30). As their study suggested an accelerating rate of induction up to the maximum dose delivered (20mcg/min), to allow for the potential effect of our study using the sulphate form of the drug rather than the hydrochloride and given the documented favourable tolerability profile of the infusion, we have elected to add a further dose increment to our protocol. This remains within the FDA approved dosing regimen for the drug.

The protocol will be..

- Infusion started at 5mcg per minute for 2 minutes
- Increased to 10mcg per minute for 2 minutes
- Increased to 15mcg per minute for 2 minutes
- Increased to 20mcg per minute for 2 minutes
- Increased to 25mcg per minute for 2 minutes
- Infusion is then stopped and subject is monitored over a 10 minute washout phase

Subjects will either follow the protocol to its completion or will reach one of the pre-defined infusion endpoints at which point the infusion will be stopped. These endpoints as described previously are..

Outcome after which infusion would be stopped

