- Occurrence of atrial fibrillation lasting greater than 30 seconds during study drug infusion protocol
- Occurrence of an arrhythmia other than atrial fibrillation, sinus tachycardia or junctional rhythm lasting greater than 30 seconds during study drug infusion protocol
- Discontinuation of the study drug infusion
 - Severe tremulousness or anxiety
 - Complaints of severe chest tightness
 - Decrease in systolic blood pressure to consistently < 70mmHg
 - Electrocardiographic changes suggestive of myocardial ischaemia

The diagnosis of atrial fibrillation will rest with the clinician acting as operator for the procedure aided by the attending cardiac physiologists.

If a subject experiences an arrhythmia lasting greater than 30 seconds and thus triggering the infusion to stop, they will be monitored for 10 minutes. It is anticipated from previous literature that in the majority of cases, subjects will have spontaneously reverted to normal sinus rhythm after this period of time. It is accepted however that in some cases an arrhythmia will persist beyond this point and in those cases, the supervising physician will restore sinus rhythm.

All subjects will be monitored for at least 30 minutes after an infusion administration.

At all infusions, the following data will be recorded

- Level of sedation at the start of the infusion (AVPU score)
- Total dose of sedation given in the 20 minutes prior to the start of the infusion

- The presence or absence of an episode of arrhythmia lasting greater than 30 seconds
 - The diagnosis for the arrhythmia seen
 - The time from initiation of the infusion to the start of the episode of arrhythmia lasting greater than 30 seconds
 - The time from the start of the episode of arrhythmia lasting greater than 30 seconds to the restoration of sinus rhythm
 - The method of restoration of sinus rhythm
- The presence or absence of one of the other reasons for stopping the infusion
 - The reason for stopping the infusion
- The time from the start of the infusion to its cessation for whatever reason
- The maximum rate of infusion delivered to the study subject
- Minute by minute heart rate and blood pressure measurements over the course of the infusion
- The presence of episodes of arrhythmia lasting less than 30 seconds
 - The diagnosis for each arrhythmia seen
 - The time from initiation of the infusion to the start of each episode of arrhythmia lasting less than 30 seconds

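### In Experiments 2 to 4 the "maximum tolerated rate" counts a stop for induced arrhythmia, the primary outcome, in the same way as a stop for intolerance

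*Protocol*

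**What the plan says.** The protocol's Study Endpoints section, under the secondary endpoints of Experiments 2, 3 and 4, lists "Maximum tolerated rate of study drug infusion prior to its cessation for any reason". The Infusion Endpoints section repeats it among the outcomes to be recorded.

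Infusion Endpoints and Infusion Protocol both give the outcomes that stop an infusion. The first two are "Occurrence of atrial fibrillation lasting greater than 30 seconds during study drug infusion protocol" and "Occurrence of an arrhythmia other than atrial fibrillation, sinus tachycardia or junctional rhythm lasting greater than 30 seconds during study drug infusion protocol". The third is discontinuation, with its own sub-list of four reasons: "Severe tremulousness or anxiety", severe chest tightness, low systolic pressure, and ECG changes suggesting ischaemia.

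The frequencies of the first two outcomes are the two primary endpoints of Experiments 2 to 4.

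The data list at the end of Infusion Protocol includes "The reason for stopping the infusion" and, as a separate item, the maximum rate delivered, without the word tolerated.

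**The concern.** The endpoint's label and its rule disagree. The label speaks of tolerance, but the rule takes the highest rate reached before any stop. An arrhythmia stop lowers the value exactly as an intolerance stop would.

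The protocol does not treat induced arrhythmia as a failure to tolerate the drug. Under Administration of Isoprenaline it describes induction of tachyarrhythmia as what the project sets out to do, and Infusion Endpoints keeps it apart from the discontinuation sub-list.

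AF is expected mostly on isoprenaline, so the rule builds the primary outcome into a secondary measure that is named as tolerability. A difference between arms would then mix two things: how often the drug induces arrhythmia, and how well it is borne. The more effective the drug is at inducing AF, the worse its tolerated rate appears, even if nobody has a symptom.

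**Working it through.** The protocol states no figure for this endpoint. The check takes the planned AF rates, applies the endpoint rule to the infusion schedule, and sets true intolerance to zero in both arms.

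**Inputs**
- AF rates, from Sample Size Calculation (Pulmonary Vein Isolation Group): 30% on isoprenaline, 1% on placebo.
- Steps, from Infusion Protocol: 5, 10, 15, 20 and 25 mcg/min, two minutes each, the last being "Increased to 25mcg per minute for 2 minutes". On placebo these are nominal rates.
- Assumptions: no intolerance stops; no stops for other arrhythmias, as the protocol gives no planning rate for them; the same mean rate at an AF stop, *m*, in both arms.

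**The planning rates.** The usual two-proportion formula (pooled variance under the null, no continuity correction, two-sided 5%, 90% power) gives 31 per arm for 1% against 30%. This matches the protocol's figure.

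**Formula.** Completers score 25, and participants stopped for AF score *m* on average. With AF rate *p*:
- arm mean = 25 × (1 − p) + p × m
- gap = (0.30 − 0.01) × (25 − m) = 0.29 × (25 − m)

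**Results**

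| Distribution of AF stops (assumed) | m | Isoprenaline | Placebo | Gap |
|---|---|---|---|---|
| Even over the five steps | 15.0 | 22.0 | 24.9 | 2.9 |
| Weighted 1:2:3:4:5 to later steps | 18.3 | 23.0 | 24.9 | 1.9 |
| All at the first step | 5.0 | 19.0 | 24.8 | 5.8 |
| All at the last step | 25.0 | 25.0 | 25.0 | 0 |

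First row in full: 25 × 0.70 + 0.30 × 15 = 22.0; 25 × 0.99 + 0.01 × 15 = 24.9; gap 0.29 × 10 = 2.9.

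Second row: m = (5×1 + 10×2 + 15×3 + 20×4 + 25×5)/15 = 275/15 = 18.3; gap 0.29 × 6.67 = 1.9.

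**Other planning rates.** Study Objectives gives a placebo rate below 5% for Experiments 2 and 3. At 30% against 5% the gap is 0.25 × (25 − m): 2.5 for even stops, 1.7 for later-weighted stops, range 0 to 5.0. Experiment 4 expects below 10% against below 5%. At those limits the gap for even stops is 0.05 × 10 = 0.5.

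**After the fix.** If tolerability is read only from stops under the discontinuation sub-list, and nobody is intolerant, both arms show none and the difference is 0.

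**The case against.** The strongest reply is that the words for any reason openly define a highest rate reached. On this view tolerated is only a loose label. The Statistical analysis section describes no between-arm test of this endpoint and no scoring rule. The reason for stopping is recorded, so an analyst can separate the stops, and an analysis plan that is not shown may do so. The Safety Assessment section also lists tachyarrhythmias among the drug's common reactions, so letting an arrhythmia limit the rate is not absurd.

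Much of this stands, and it is why the point is small. It does not remove the point. The protocol is not silent here: it fixes the rule, and an analysis plan that separated the stops would depart from the endpoint as written. The protocol also keeps arrhythmia apart from discontinuation in its own list.

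The size is also open to challenge. Infusion Protocol reports that induction accelerated with dose in the earlier study, which favours later stops and the lower part of the range. A gap near 8 mcg/min needs an AF rate of about 80% with even stops (0.79 × 10 = 7.9). The Sample Size Calculation says the literature rate above 80% does not fit the investigators' own practice.

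A reader might infer three stronger things, which the protocol does not support:
- *That AF in the washout scores zero.* Infusion Protocol says of the end of the last step: "Infusion is then stopped and subject is monitored over a 10 minute washout phase". Someone whose AF starts then has completed every step and scores 25 on this endpoint. Zero arises only for a different endpoint, "Rate of infusion at time of occurrence of atrial fibrillation", and only on a literal reading. The protocol writes no such value, and the coding can be left to an analysis plan.
- *That Experiments 1, 5 and 6 share the fault.* Their endpoint is a change in maximum rate between two infusions. It does not say tolerated and makes no tolerability claim.
- *That later use of the infusion scheme would rest on this endpoint.* The section on future application builds on inducibility and non-inducibility, not on tolerated rate.

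**Conclusion.** The point holds for one secondary endpoint of Experiments 2 to 4 and is minor. As written, the tolerated rate falls when the primary outcome occurs, so isoprenaline can appear less well tolerated with no intolerance at all. At 30% against 1% AF the spurious gap is about 2.9 mcg/min for stops spread evenly and about 1.9 for stops weighted to later steps, within a possible range of 0 to 5.8. These figures rest on an assumed distribution of AF stops, no intolerance in either arm, and no stops for other arrhythmias. No primary conclusion, sample size or interim rule depends on the endpoint. Nothing here calls for a change to the infusion schedule or the stopping rules.

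**What to change.** Rename the endpoint *maximum rate delivered* and report it by reason for stopping: completed, AF, other arrhythmia, or discontinuation. Base any statement about tolerability only on stops under the discontinuation sub-list. Show arrhythmia stops beside them, because a participant stopped for arrhythmia had no chance to show intolerance at a higher step. Reporting by reason is enough. Treating arrhythmia stops as censored would add the assumption that arrhythmia is unrelated to later intolerance, although both may be effects of the drug.

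The cost is a change of wording in Study Endpoints and Infusion Endpoints, carried into the analysis plan. The reason for stopping and the maximum rate are already recorded, so no new data are needed.

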This protocol will also collect data regarding the inducibility of atrial fibrillation by an isoprenaline infusion in participants prior to atrial flutter and SVT ablation and after a pulmonary vein isolation procedure. In the pulmonary vein isolation group this will allow analysis of the change in inducibility associated with that procedure. These data will be reported as secondary, hypothesis generating experimental analyses and hence are not associated with detailed power calculations as in the defined analyses above.

Study Design

This project investigates different aspects of the use of isoprenaline to induce an occurrence of atrial fibrillation through a number of different experiments. Data from any one participant may be used in a number of the experimental analyses, however participation in the study will follow one of 2 schedules for any given subject. As this is the case the project has been presented in two parts, with participants in Part A sharing a similar experience which will be different to those participating in Part B and vice versa.

Of note, where eligible, subjects will be offered the opportunity to participate in more than one part of the study. For example, a participant with a diagnosis of paroxysmal atrial fibrillation could take part in Protocol Part A and then go forward for an ablation procedure, associated with which they could take part in Protocol Part B. To avoid possible contamination of results, this will not be allowed where it will mean that study drug infusions for different parts of the study will occur closer than 2 weeks apart.

Protocol Part A

This part of the project investigates the consistency of the outcome of repeated administrations of an isoprenaline infusion. Subjects for this part will be recruited independent of their need for an ablation procedure. The isoprenaline, study drug infusion is administered on an open label basis on two separate occasions at least 2 weeks apart. Administration will be in a ward based environment. No follow up visits will be required.

Protocol Part B

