At the end of the visit, he participant will be invited to schedule Visit 2, the "First Isoprenaline Infusion Administration Visit", at a time which is convenient for them. They will be asked to stop antiarrhythmic drugs 6 half-lives prior to the visit and be asked to starve for 6 hours prior to it also.

Schedule for participants involved in Protocol Part A								
Study Procedure	NHS clinical review and / or subsequent telephone conversation (Enrolment)		Visit 2 (First Isoprenaline Infusion Administration)	Visit 3 (Repeat Isoprenaline Infusion Administration)				
Identification of possible suitable subject	x							
Subject given written information and approached about study	х							
Eligibility assessment		х						
Informed Consent		х						
Demographic data collection		x						
Medical history data collection		х						
Observations (to include pulse, BP, SpO ₂ , Weight)			х	x				
12 lead ECG		х	х	x				
Serum taken for analysis (Optional)		x	х	x				
Open label Isoprenaline infusion administration			x	x				
Total visit time	20 mins	20 mins	3 hours	3 hours				
Study measurements / Consultation time	5 mins	20 mins	45 mins	45 mins				

• Part A – Visit 2 – First Isoprenaline Infusion Administration

All subjects will have been asked to stop antiarrhythmic drugs 6 half-lives prior to this visit and have been asked to starve for 6 hours prior to their visit. This will be confirmed with the subject at this point.

If a participant is experiencing an episode of atrial fibrillation at the time of attending for either Visit 2 or 3 they will not be able to go ahead with the infusion administration. The study team will confirm that the participant wishes to remain involved in the study and if they do, they will be asked to reattend on another occasion. If they re-attend, again in atrial fibrillation, they will be withdrawn from the study as it is not felt to be in their best interests to continue.

Measurements will be taken of basic physiological observations including pulse rate and rhythm, blood pressure from both arms, oxygen saturations, weight in kilograms and height in metres. All subjects will undergo 12 lead ECG recording. Where the optional consent is provided, blood samples will be taken.

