Participants will be monitored for at least 30 minutes after the end of the infusion protocol. At this point they will have their basic physiological observations repeated to include pulse rate and rhythm, blood pressure and oxygen saturations. Release from hospital will be at the discretion of the supervising clinician. It is anticipated that a small number of subjects will be required to remain under observation for a number of hours especially in the context of the need for sedation and cardioversion for subjects who remain in persistent arrhythmia following the infusion.

At release from this visit, subjects will be advised to restart any antiarrhythmic agents which they had withheld as part of the study protocol for this visit. They will also be provided with contact information for the study team and advised that they should contact the team with any concerns or problems following their participation in the project. The conclusion of this visit represents the end of their participation in the study.

Study Procedure - Protocol Part B

This part of the protocol involves participants who will have been recruited as they are undergoing an ablation procedure on the NHS. The SVT ablation, atrial flutter ablation and the pulmonary vein isolation groups will be recruited to this part of the study.

The study infusion will be delivered in a double blinded, randomised manner. Each participant group will undergo 1 to 1 randomisation to receive either an isoprenaline infusion at the start and end of their ablation or the placebo infusion at the start and end.

Part B of the protocol will require a minimum of 4 encounters with the study team. For subjects who have given consent to undergo additional ECG monitoring, the study schedule requires 7 visits over the 12 months. Usual NHS care for all participants enrolled to Part B of the protocol would involve 4 visits to hospital, one of these may not be required by the study participants and 3 are combined with study visits.

Schedule for participants involved in Protocol Part B								
Study Procedure	NHS clinical review and / or subsequent telephone conversation	Visit 1 (Enrolment)	Visit 2 (Ablation Procedure)	Visit 3 (6 week F/U)	Visit 4 (3 month F/U)			
Identification of possible suitable subject	x							
Subject given written information and approached about study	x							
Eligibility assessment		х						
Informed Consent		х						
Demographic data collection		х						
Medical history data collection		х						

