The investigators are authorised to provide alternative treatment to that specified in the protocol at any stage if he/she feels it is in the participant's best interest. The reasons for deviation from protocol should be recorded.

Reasons for Discontinuation of Subject's Participation in Study

A subject can voluntarily discontinue their involvement in the study at any stage without the need to give reason and without prejudicing further treatment. In addition, subjects will be removed from the study if they cease to meet the inclusion criteria after enrolment (eg participant in SVT block has electrophysiology study that demonstrates atrial tachycardia rather than ANRT or AVNRT) or if they develop one of the exclusion criteria (eg require treatment with amiodarone in the time between the 2 infusions required for Protocol Part A). Subjects will also be excluded from continuation in the study if they develop anaphylaxis, chest pain or ECG features of myocardial ischaemia during the infusion protocol.

Where subjects withdraw or are excluded from the study after enrolment but prior to their completion of the study schedule, a further subject will be recruited to their subject group to take their place. Any data collected before withdrawal may be included in the study results.

End of Study Actions

Having withdrawn from the study, been excluded from continued participation or having completed their final visit or ambulatory ECG recording, participants will have completed their involvement in the study. There are no specific interventions required at completion of the study schedule. All participants will be informed that they may still contact the study team should they have questions or concerns regarding their health or their involvement in the study.

Safety Assessment

Adverse Events

Definitions

- Adverse Event (AE): any untoward medical occurrence in a patient or clinical study subject.
- Serious Adverse Event (SAE): any untoward and unexpected medical occurrence or affect that:
 - Results in death
 - Is life-threatening refers to an event in which the subject was at risk of death at the time of the event; it does not refer to an event which hypothetically might have caused death if it were more severe
 - Requires hospitalisation, or prolongation of existing inpatients' hospitalisation
 - Results in persistent or significant disability or incapacity
 - o Is a congenital anomaly or birth defect

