It is noted that this study runs alongside standard NHS care for many participants which includes a cardiac catheter ablation procedure. It is anticipated from registry data regarding the rate of complication(53)(54) associated with such procedures will mean that some participants will experience them. Below is a list of serious adverse events which may occur during the study but

which the investigators would expect that, upon full review, would be linked with the ablation procedure, rather than the administration of the study drug protocol.

- Cardiac Tamponade or Perforation
- Vascular Access Complication
- Haematoma
- Pulmonary Vein Stenosis
- Atrio-Oesophageal Fistula formation

Un-blinding Procedure

If, in the context of a medical emergency, the clinical team caring for the participant require unblinding as to the contents of the study drug infusion, this will occur immediately. The most simple method for this to occur is that the un-blinded nurse who drew up the study drug can be asked directly to inform the clinical team and / or investigators as to the contents of the infusion. It is anticipated that the nurse will remain be in the room for the duration of the infusion in all cases but will not take part in any of the subsequent study procedures or observations.

If the nurse is unsure as to the contents of the infusion for any reason, or if the nurse who drew up the study infusion is not present for any reason, the participant's study number can be correlated with the instructions in the randomisation folder from which the un-blinded nurses will determine which infusion to draw up. This document will be kept within the cardiac electrophysiology laboratory and so will be available immediately.

Un-blinding will always be reported as a serious adverse event.

Reporting procedure

All adverse events should be reported. Depending on the nature of the event the reporting procedures below should be followed. Any questions concerning adverse event reporting should be directed to the Chief Investigator in the first instance. All project team members will be GCP trained.

All such events, whether expected or not, should be recorded in the CRF. In the event of an adverse event/reaction, a member of research team will:

- Review all documentation (e.g. hospital notes, laboratory and diagnostic reports) relevant to the event
- Record the event and relevant comments in the subject's medical notes (or source data where this is not the medical notes)

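### After the second Part A infusion, no active check covers the rest of the 24-hour death, stroke and MI window; separately, the SAE definition wrongly requires events to be unexpected

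*Protocol*

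**What the plan says.** Under Infusion Endpoints, the protocol lists safety endpoints for each infusion, beginning with "Death within 24 hours of start of study drug infusion protocol". Stroke and MI follow with the same window. The same section says that "the endpoints for every administration of a study drug infusion protocol are the same", so the open-label Part A infusions are covered.

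For Part A, the Study Design section states: "No follow up visits will be required". The Visit 3 text says: "Participants will be monitored for at least 30 minutes after the end of the infusion protocol". It then gives participants the team's contact details, advises them to get in touch about concerns, and closes with: "The conclusion of this visit represents the end of their participation in the study". In the Part A schedule, the row "Total visit time" shows 3 hours for each infusion visit.

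The section on reasons for discontinuation excludes from continuation anyone with chest pain or ECG features of ischaemia during an infusion. End of Study Actions treats excluded participants as having completed their involvement.

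Under Safety Assessment, Definitions, an SAE is "any untoward and unexpected medical occurrence or affect that" meets one of the usual seriousness criteria. Later in Safety Assessment, a list of anticipated ablation complications opens with the words "Below is a list of serious adverse events which may occur during the study but", and the sentence goes on to link them to the ablation rather than the infusion. The reporting section has investigators assess expectedness and seriousness as separate attributes of every event.

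**The concern.** An endpoint with a 24-hour window needs some planned step that looks at the participant's status once 24 hours have passed. For the second Part A infusion there is none: the participant formally leaves the study on the same day. The remaining route depends on the participant making contact. It cannot report that participant's own death, and it is unreliable for a disabling stroke. If the report shows no events after these infusions, the reader cannot tell from the planned procedures how far that reflects absence and how far it reflects not asking. An analysis plan cannot repair this, because the visit schedule does not generate the data.

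Participants excluded for chest pain or ischaemic ECG changes are the ones in whom a later MI is of most interest. In Part A they lose planned follow-up at whichever infusion this happens.

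The SAE wording is a separate matter. Listed reactions such as hypotension and tachyarrhythmia are to be reported as adverse events only if they amount to an SAE or a suspected unexpected serious adverse reaction (SUSAR). If both terms require unexpectedness, a serious but listed reaction may be thought to fall under neither, and the sponsor notification due within 24 hours is then not clearly triggered.

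**Working it through.** **Observed time against the 24-hour window, second Part A infusion**

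Inputs, all from the protocol:
- infusion: five steps of 2 minutes (Infusion Protocol)
- washout: 10 minutes (Infusion Protocol)
- monitoring: at least 30 minutes after the end of the infusion protocol (Part A, Visit 3)
- planned visit: 3 hours (Part A schedule)
- window: 24 hours = 1,440 minutes from the start of infusion

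Calculations for a full-length infusion:
- Infusion = 5 × 2 = 10 min.
- Guaranteed observation, if the 30 minutes follow washout: 10 + 10 + 30 = 50 min; 50/1,440 = 3.5%; uncovered 24 − 0.83 = 23.17 h.
- If the 30 minutes run from the end of the infusion itself: 10 + 30 = 40 min; 40/1,440 = 2.8%; uncovered 24 − 0.67 = 23.33 h.
- Whole planned visit counted as observation: 180/1,440 = 12.5%; uncovered 24 − 3 = 21 h. This is generous, since part of the visit precedes the infusion.

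So about 21 to 23 hours fall after participation has ended.

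**How many windows**

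- The Part A size can be reproduced: 1.96² × 0.10 × 0.90 / 0.10² = 34.6, rounded up to the stated 35. It is used here only as a count.
- Part A windows: 35 × 2 = 70. Those closing after the end of participation: 35, or 50%.
- Trial-wide: the planned 235 participants, assumed to have two infusions each, give 470 windows; 35/470 = 7.4%. Some flutter participants will miss the pre-ablation infusion, so 470 is an upper figure.
- Early exclusions at the first Part A infusion would add to the 35. The protocol gives no rate from which to count them.

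**Other infusions**

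- First Part A infusion: the participant remains enrolled and returns at least 2 weeks later, but the schedule lists no enquiry about events in between.
- Part B: participants remain to at least 3 months and have a follow-up interview.

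**SAE wording: the sections compared**

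- Definitions: an SAE must be unexpected; an adverse event need not be.
- List of ablation complications: events the investigators anticipate are called SAEs.
- Reporting procedure: all events go on the case report form (CRF) whether or not expected, and expectedness is judged separately from seriousness.
- Death, stroke and MI appear neither in the table of drug reactions nor in the list of ablation complications.

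The first entry cannot be squared with the second and third. The fourth shows that the three 24-hour endpoints would still meet the SAE definition as written.

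**The case against.** The best defence has four parts.

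- **Scope.** Only the second Part A infusion and early exclusions lack later planned contact. That is about 7% of infusion windows, and no hypothesis, sample size or primary analysis uses these endpoints. This stands and limits the severity.
- **Information.** Even with perfect capture, zero events in 35 infusions leaves a one-sided 95% upper limit of 1 − 0.05^(1/35) = 8.2%. This also stands. Part A can say little about rare events, but that does not justify naming an endpoint and not planning to ascertain it.
- **Existing routes.** Participants have contact details and are advised to use them, and hospital notes are a data source. A reader might infer that there is no later contact at all, or that an unknown outcome would be entered as no event. The protocol supports neither: the route exists but is passive, and no rule is given for coding an unascertained endpoint. Nor is any check of the notes at 24 hours scheduled.
- **SAE wording.** A reader might infer that the unexpectedness condition also makes the trial miss its 24-hour endpoints. It does not. Those endpoints are named independently, are on neither expected list, and are covered by CRF recording. The medical-judgement clause also lets important events be treated as serious without regard to expectedness. One caveat is that the risk section mentions possible MI where obstructive coronary disease coexists, so an investigator might call an MI expected; that would affect SAE reporting, not recording. The contradiction in the definition remains.

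**Conclusion.** The point holds in limited form. For all 35 planned Part A completers, about 21 to 23 hours of the 24-hour window after the second infusion have no planned active ascertainment. The same is true of Part A participants excluded for chest pain or ischaemic ECG features at either infusion. This assumes that visits run close to the planned 3 hours; the protocol expects a small number to stay longer under observation, and their gap would be shorter. The finding does not extend to Part B. For those who continue after the first Part A infusion, the gap is only that no question about interval events is listed at Visit 3.

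The SAE definition is a separate internal contradiction. Its effect is on the clarity of expedited reporting of serious listed reactions, and its size cannot be calculated from the protocol. These are descriptive safety outcomes on which no primary analysis depends. The changes should be made, but the trial's main conclusions do not turn on them.

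**What to change.** - Schedule a short scripted telephone contact or record check at or after 24 hours following the second Part A infusion, and following any infusion after which a Part A participant is excluded. It should cover death, stroke, MI and hospital attendance.
- Define the end of Part A participation, including for excluded participants, as completion of that contact or check.
- Add a question at Visit 3 on events in the 24 hours after the first infusion.
- Delete the words *and unexpected* from the SAE definition, and keep expectedness for SUSAR classification only.

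The cost is about 35 short contacts by existing staff, plus any for early exclusions, and at most about 70 if the team prefers one after every Part A infusion. A few lines of protocol text change. No dose, sample size or primary endpoint is affected.
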